6.1.2. Statistical Hypothesis for the Key Efficacy Endpoint

The null (H₀) and alternative (H₁) hypotheses used to assess the superiority of SOF + RBV relative to the historical SVR12 rate of 80% are as follows:

H₀: SVR12 rate = 80%

H₁: SVR12 rate ≠ 80%

6.1.3. Analysis Methods for the Key Efficacy Endpoint

A sequential test method was used to firstly perform the above statistical test in the adolescent subjects (ie, 12 to < 18 years of age). The SVR12 rate for adolescents was compared with the historical SVR12 rate of 80% using a 2-sided exact 1-sample binomial test at the 0.05 significance level. The test in adolescents was described in a separate SAP for Adolescents SVR12 Analysis. Only if the superiority is demonstrated in adolescents, the SVR12 rate in the remaining subjects (ie, children aged 3 to < 12 years) will be compared with 80% at the 0.05 significance level.

The point estimates of SVR12 rate and 2-sided 95% exact CI based on Clopper-Pearson method will be provided for the SVR12 rate by treatment group and total in each age group {Clopper 1934}.

6.1.4. Subgroup Analysis of the Key Efficacy Endpoint

The point estimates of SVR12 rate and 2-sided 95% exact CIs based on Clopper-Pearson method will be provided for each treatment group within each subgroup specified in Section 3.4 {Clopper 1934}.

A Forest plot will graphically present estimates and 95% confidence intervals of SVR12 rates for each treatment group within each subgroup.

6.2. Secondary Efficacy Endpoints

6.2.1. Definition of Secondary Efficacy Endpoints

Secondary efficacy endpoints include the following:

- The percentage of subjects who attain SVR at 4 and 24 weeks after stopping therapy, defined as HCV RNA < LLOQ (i.e. < 15 IU/mL) 4 and 24 weeks after stopping treatment (SVR 4 and SVR 24)
- The percentage of subjects with HCV RNA below LLOQ by study visit
- HCV RNA (\log_{10} IU/mL) and change from baseline in HCV RNA (\log_{10} IU/mL) through end of treatment (EOT)
- The percentage of subjects with virologic failure as the following:

On-treatment virologic failure

- HCV RNA \geq LLOQ after having previously had HCV RNA < LLOQ, while on treatment, confirmed with 2 consecutive values (note, second confirmation value can be posttreatment), or last available on-treatment measurement with no subsequent follow-up values (i.e. breakthrough)
- $> 1 \log_{10}$ IU/mL increase in HCV RNA from nadir while on treatment, confirmed with 2 consecutive values (note, second confirmation value can be posttreatment), or last available on-treatment measurement with no subsequent follow-up values (i.e. rebound)
- HCV RNA persistently \geq LLOQ through 8 weeks of treatment (i.e. nonresponse)

Relapse

- HCV RNA \geq LLOQ during the posttreatment period having achieved HCV RNA < LLOQ at end of treatment, confirmed with 2 consecutive values or last available posttreatment measurement
- The proportion of subjects with ALT normalization (defined as ALT > ULN at baseline and ALT \leq ULN at each visit), presented by study visit.
- Characterization of HCV drug resistance substitutions at baseline, during, and after therapy with SOF

6.2.2. Analysis Methods for Secondary Efficacy Endpoints

For analyses of HCV RNA < LLOQ by visit while on treatment and during the posttreatment (SVR) follow-up period, subjects will be assigned a value at each visit based on the analysis visit windows specified in Section 3.7.2. Missing values will be imputed based on the categorical imputation rules described in Section 3.5.1. The 2-sided 95% exact confidence interval based on Clopper-Pearson method will be provided for the percentage of subjects with HCV RNA < LLOQ at each visit in each treatment group. The overall category for “HCV RNA < LLOQ” will be split into the following 2 subcategories: “< LLOQ TND” for subjects with target not detected and “< LLOQ detected” for subjects with < LLOQ detected in tabular displays.

Graphs for the percentage of subjects with HCV RNA < LLOQ over time during treatment will be displayed.

Summary statistics will be presented for absolute values and change from baseline in HCV RNA (\log_{10} IU/mL) by visit through EOT. Imputation rules described in Section 3.5.1 will be used to assign HCV RNA values for missing values at a visit that are bracketed by “< LLOQ TND” and/or “< LLOQ detected”. Otherwise, a missing = excluded analysis will be performed. Plots of the mean \pm SD and median (Q1, Q3) of absolute values and changes from baseline in HCV RNA through EOT will be presented.

For the SVR12 endpoint analysis, a summary table of the number and percentage of subjects with SVR12, virologic failure (VF), and Other will be created. All subjects who achieve SVR12 will be categorized as SVR12. Virologic failure will be descriptively summarized as “on-treatment virologic failure” and relapse (which will be broken down by study drug completed yes/no). Subjects who do not achieve SVR12 and do not meet criteria for VF will be categorized as Other. The denominator for relapse will be the number of subjects who had HCV RNA < LLOQ on their last observed on-treatment HCV RNA measurement; otherwise, the denominator will be the number of subjects in the FAS. Additional summary table will be provided by treatment group defined in Table 3-2 for 3 to < 6 years of age subjects.

A concordance table between SVR12 and SVR24 will be provided by treatment group and total in each age group. Subjects with both observed SVR12 and observed SVR24 data will be included for this analysis.

In addition, a summary table of the number and percentage of subjects with HCV RNA < LLOQ and \geq LLOQ at the posttreatment follow-up visit (observed and imputed, with reasons for imputed) will be provided for each posttreatment follow-up visit. 95% Clopper-Pearson exact CIs will be presented for the overall proportion of subjects with HCV RNA < LLOQ.

Tables for ALT normalization by visit will use similar methodology to the analyses of HCV RNA < LLOQ, but will use a missing = excluded analysis. Only those subjects with ALT greater than the ULN range at baseline (defined as the last ALT value collected prior to first dose of study drug) will be included in the analysis of ALT normalization.

Drug resistant substitutions will be analyzed as part of the Virology Study Report.

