### 9.1.3. Secondary Endpoints

For the PK Lead-in Phase, the secondary endpoints include antiviral activity measurements, including assessment of HCV RNA. AEs leading to permanent discontinuation of study drug(s) will be evaluated as a secondary safety endpoint.

For Treatment Phase, secondary efficacy endpoints include SVR4, SVR24, breakthrough and relapse. Additional efficacy evaluations may include HCV RNA change from Day 1; ALT normalization; viral kinetic parameters, and palatability of SOF oral granules. Secondary safety endpoints of growth and development measurements will be assessed (e.g. height, weight, and Tanner Stage Assessment).

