4. SUBJECT DISPOSITION

4.1. Subject Enrollment and Disposition

A summary of subject enrollment will be provided by treatment group for each country, investigator within a country, and overall. The summary will present the number and percentage of subjects in the Safety Analysis Set. For each column, the denominator for the percentage calculation will be the total number of subjects analyzed for that column.

A summary of subject disposition will be provided by treatment group. This summary will present the number of subjects screened, the number of subjects enrolled, the number of subjects enrolled but never treated, and the number and percentage of subjects in each of the categories listed below. For the “Treated” category, the denominator for the percentage calculation will be the total number of subjects enrolled for each column. For all other categories, the denominator for the percentage calculation will be the total number of subjects in the Safety Analysis Set for each column.

- Treated (Safety Analysis Set)
- In FAS
- In PK Analysis Set
- Completed study treatment
- Did not complete study treatment with reasons for premature discontinuation of study treatment
- Completed the study
- Did not complete the study with reason for premature discontinuation of study

Among subjects who completed study treatment and who discontinued study treatment, the number and percentage of subjects will be summarized for:

- Who had no HCV posttreatment Week 4 assessment and thereafter (No HCV FU-4 and thereafter)
- Who had HCV posttreatment Week 4 assessment but no HCV posttreatment Week 12 assessment and thereafter (With HCV FU-4 but No FU-12 and thereafter)

If a subject did not have any HCV RNA assessment ≥ 21 days after the last dose of any study drug (i.e. lower bound of FU-4 visit for HCV RNA data), the subject is categorized as having “No HCV FU-4 and thereafter”. If a subject had the HCV FU-4 assessment but did not have any HCV RNA assessment ≥ 70 days after the last dose of any study drug (i.e. lower bound of FU-12 visit for HCV RNA data), the subject is categorized as having “With HCV FU-4 but No FU-12 and thereafter”.

In addition, the total number of subjects who were enrolled, and the number of subjects in each of the disposition categories listed above will be displayed in a flowchart.

The following by-subject listings will be provided by subject ID number in ascending order to support the above summary tables:

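### The only relapse rate in the SAP leaves out a subject who achieves SVR12 and is viraemic at post-treatment Week 24, although the SAP's own definition counts that subject as a relapse

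*SAP*

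**What the plan says.** Protocol 9.1.3 makes relapse an endpoint in its own right: "For Treatment Phase, secondary efficacy endpoints include SVR4, SVR24, breakthrough and relapse".

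SAP 6.2.1 defines relapse as HCV RNA at or above "LLOQ during the posttreatment period having achieved HCV RNA < LLOQ at end of treatment". As to what establishes it, the same definition requires that the finding be "confirmed with 2 consecutive values or last available posttreatment measurement". There is no Week 12 cut-off.

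SAP 6.2.2 gives the method. Relapse appears inside the outcome table for SVR12, which has three exclusive categories: SVR12, virologic failure and Other. SVR12 takes precedence: "All subjects who achieve SVR12 will be categorized as SVR12". Within the failure category, "Virologic failure will be descriptively summarized as “on-treatment virologic failure” and relapse". The denominator is also set there: "The denominator for relapse will be the number of subjects who had HCV RNA < LLOQ on their last observed on-treatment HCV RNA measurement". An additional table for ages 3 to < 6 years has the same layout by weight group. No other relapse rate is specified.

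HCV RNA is collected at post-treatment Week 24 (Protocol 6.5.3). SAP Table 3-4 gives that visit a window of follow-up days 147 to 210, and SAP 2.2 holds the final analysis until subjects have completed it or left the study.

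**The concern.** The definition and the tabulation cover different periods. The definition runs to the end of follow-up. The table effectively stops at SVR12, because a subject who has reached SVR12 can no longer be placed in the failure category. The data needed to apply the full definition are collected and are in hand at the time of analysis.

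What is at stake is the meaning of a reported secondary endpoint. A reader of the study report would take the row called relapse to be the quantity defined in 6.2.1. It is in fact relapse among subjects who did not achieve SVR12. Relapse after Week 12 is the part that SVR12 cannot show, so it is the part for which a separate relapse endpoint adds information.

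**Working it through.** The documents state no relapse rate, late-relapse rate or loss-to-follow-up rate, so there is no planned figure to reproduce. The check is to follow one subject through the rules and then show the arithmetic with assumed counts.

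**One subject through the rules.** Take a subject below LLOQ at the end of treatment and at follow-up Week 12 (FU-12), and at or above LLOQ at follow-up Week 24 (FU-24), the last value available.

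- SAP 6.2.1: relapse, because the value falls in the post-treatment period and is the last available measurement.
- SAP 6.2.2, category: SVR12, by the precedence rule, so not virologic failure and not relapse.
- SAP 6.2.2, denominator: included, because the last on-treatment value was below LLOQ.

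The subject is in the denominator, meets the definition, and is missing from the numerator.

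**How wide the gap is.** The FU-12 window for HCV RNA runs from follow-up day 70 to 146 (SAP Table 3-4), and the latest record in the window is used (SAP 3.7.3). If the latest record up to day 146 is at or above LLOQ, the subject fails SVR12 and can be counted. If FU-12 is missing and FU-24 is at or above LLOQ, the missing value is imputed as a failure (SAP 3.5.1), so that relapse can also be counted. The gap is confined to subjects who have SVR12 and are viraemic later.

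**Formula.** Let N be the subjects below LLOQ at the last on-treatment test, r the relapses among subjects without SVR12, and L the subjects with SVR12 who later meet the relapse definition.

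- As tabulated: r/N.
- By the 6.2.1 definition with the SAP's own denominator: (r + L)/N.
- Difference: L/N, which is never negative.

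**Results.** All counts are assumptions. N of 48 to 50 corresponds to one age group of about 50 subjects, and N = 100 to the whole study.

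| N | r | L | As tabulated | By definition |
|---|---|---|---|---|
| 48 | 5 | 1 | 5/48 = 10.4% | 6/48 = 12.5% |
| 50 | 2 | 1 | 2/50 = 4.0% | 3/50 = 6.0% |
| 50 | 0 | 1 | 0/50 = 0% | 1/50 = 2.0% |
| 100 | 2 | 1 | 2/100 = 2.0% | 3/100 = 3.0% |
| 50 | 2 | 0 | 2/50 = 4.0% | 2/50 = 4.0% |

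Each late relapse is worth about 2 percentage points in an age group and 1 point overall. It is worth more within an age-by-genotype group, where N is smaller.

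**The case against.** The best defence is that the table is introduced as part of the SVR12 analysis. It divides subjects by SVR12 outcome, and the division works only if SVR12 takes precedence. That is right, and the table should stay as it is. It does not answer the point that 6.2.2 offers no other relapse rate.

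A second defence is that late cases are not hidden. The concordance table between SVR12 and SVR24 (SAP 6.2.2) has a cell for SVR12 achieved and SVR24 not achieved. The table of results below and at or above LLOQ at each follow-up visit includes FU-24. Both would show the case, and a careful reader could add it by hand. Neither is labelled relapse or changes the relapse rate.

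A third is that the effect is likely to be small. SAP 3.5.1 relies on a high correlation between SVR12 and SVR24, the FU-12 window already reaches day 146, and the row is descriptive, with no test or decision attached. This stands, and it limits the weight of the point.

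A reader might go further and infer that the denominator is also wrong, because it keeps subjects with no HCV RNA after treatment, who cannot be seen to relapse. The documents do not support calling that an error. The definition in 6.2.1 sets no denominator, and 6.2.2 states the only one. Subjects who are never tested count as SVR12 failures, fall under Other in the outcome table, and are counted in disposition (SAP 4.1: "Who had no HCV posttreatment Week 4 assessment and thereafter"). Removing them is a complete-case choice that treats them as relapsing at the same rate as those tested, which nothing in the documents establishes. Its effect alone is also modest: with N = 50 and r = 2, dropping 2 or 5 untested subjects moves 4.0% to 2/48 = 4.2% or 2/45 = 4.4%, and with no counted relapse it moves nothing.

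**Conclusion.** The concern holds for the numerator. The relapse rate specified in SAP 6.2.2 does not match the relapse definition in SAP 6.2.1, and the mismatch can only lower the rate. The size is L/N: 10.4% against 12.5% in the main illustration. This depends on at least one subject with SVR12 becoming viraemic by FU-24; with none, the two rates are identical. The documents give no basis for predicting how many such cases there will be, and the SAP itself expects few.

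The SVR12 estimate and its test against 80% are unaffected. This is a mismatch between definition and table that is worth correcting because doing so costs almost nothing. It is not a threat to the trial's main conclusions.

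**What to change.** - Keep the SVR12 outcome table and label its row *relapse among subjects without SVR12*.
- Add a row for relapse through post-treatment Week 24 that applies the 6.2.1 definition regardless of SVR12 status, by treatment group and age-group total, with the denominator already stated in 6.2.2.
- Optionally, footnote how many subjects in that denominator have no post-treatment HCV RNA. Changing the denominator is a matter of choice and not needed to correct the mismatch.

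The cost is one extra row from data already collected, and a relapse figure that may be slightly less favourable. No visit, sample or test changes.

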### 7.2. Subject Stopping Rules for SOF

The Gilead Medical Monitor should be consulted prior to dose discontinuation of SOF unless the investigator believes that immediate action is warranted to ensure the continued safety of the subject.

Administration of SOF may be discontinued due to a clinical or laboratory event. There is no option for SOF dose reduction. If SOF is stopped for toxicity, it should not be restarted, RBV should be stopped and the subject should complete an Early Termination Visit.

Subjects who meet any of the following laboratory criteria must stop treatment with SOF and RBV:

- Elevation of ALT and/or AST >5x Day 1 or nadir, confirmed by immediate repeat testing
- Abnormal elevation of ALT >3x Day 1 and total bilirubin >2 x ULN, confirmed by immediate repeat testing
- Confirmed elevation of ALT >15 x ULN
- Any Grade 3 or greater rash associated with constitutional symptoms
- Any Grade 4 event or lab abnormality assessed as related to treatment with SOF

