### 9.2.2. Data Handling Conventions

Natural logarithm transformation for key PK parameters, such as  $C_{max}$  and  $AUC_{tau}$ , will be applied for pharmacokinetic analysis.

The PK concentration values below the limit of quantitation (BLQ) will be treated as zero for the determination of summary and order statistics. Individual values that are BLQ will be presented as “BLQ” in the concentration data listing and will be excluded in any calculation of geometric means or ratios. For the presentation of summary and order statistics, if at least 1 subject has a concentration value BLQ for the time point, then the minimum value will be displayed as “BLQ”. If more than 50% of the subjects have a concentration data value BLQ for the time point, then the minimum and median values will be displayed as “BLQ”. If all subjects have concentration data values BLQ for the time point, then all order statistics (minimum, first quartile [Q1], median, third quartile [Q3], maximum) will be displayed as “BLQ”.

Missing data can have an impact upon the interpretation of the trial data. Other than the endpoints discussed below, in general, values for missing data will not be imputed.

For the analysis of post-baseline categorical efficacy endpoints, if a data point is missing and is preceded and followed in time by values that are deemed successes, then the missing data point will be termed a success; otherwise the data point will be termed a failure.

Any subject with missing data due to premature discontinuation of the study medication will be considered a failure at the time points subsequent to the date of discontinuation. If no HCV RNA values are obtained after the last dose of study medication, the subject will be considered a treatment failure for the SVR endpoints.

Where appropriate, safety data for subjects that did not complete the study will be included in summary statistics. For example,

- If a subject received study medication, the subject will be included in a summary of adverse events according to the treatment received; otherwise, if the subject is not dosed then they will be excluded from the summary.

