6.4. Changes From Protocol-Specified Efficacy Analyses

Instead of comparing the SVR12 rate in all treated subjects (3 to < 18 years of age) against the historical SVR12 rate of 80% by using the 2-sided exact 1-sample binomial test at the 0.05 significance level as specified in the protocol, a sequential test method was used to firstly perform the above statistical test in the adolescent subjects (12 to < 18 years of age). Only if the superiority is demonstrated in adolescents, the SVR12 rate in the remaining subjects (3 to < 12 years of age) will be compared with 80% at the 0.05 significance level. The test in adolescents was described in a separate SAP for Adolescents SVR12 Analysis. Details of the test in this Final Analysis are described in Section [6.1.3](#).

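### The SAP analyses ALT normalization on observed cases only, an undeclared departure from the protocol's rule that missing categorical efficacy values are failures unless bracketed by successes

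*SAP*

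**What the plan says.** - **Status of the endpoint.** SAP 6.2.1 includes "The proportion of subjects with ALT normalization" by visit among the secondary efficacy endpoints. Protocol 9.1.3 is looser ("Additional efficacy evaluations may include HCV RNA change from Day 1; ALT normalization") but still places it under efficacy, as does Protocol 9.6.2.
- **Protocol rule.** Protocol 9.2.2 states its scope as follows: "For the analysis of post-baseline categorical efficacy endpoints, if a data point is missing and is preceded and followed in time by values" that count as successes, the missing point is a success; "otherwise the data point will be termed a failure". The next paragraph makes missing data after premature discontinuation of study medication a failure at all later time points.
- **SAP rule.** SAP 6.2.2 applies HCV RNA-type methods to ALT normalization "but will use a missing = excluded analysis". The analysis population is restricted: "Only those subjects with ALT greater than the ULN range at baseline" enter.
- **SAP imputation.** The categorical imputation in SAP 3.5.1 is written for HCV RNA and does not extend to ALT.
- **Declared changes.** SAP 6.4 describes one change from the protocol's efficacy analyses, the sequential SVR12 test (adolescents first, then younger children). The ALT rule is not there.

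**The concern.** The protocol fixed a missing-data rule for a class of endpoints. The SAP replaces it for one member of that class without saying so in the section meant for such changes. The replacement also works in one direction for children who stop treatment: they leave the denominator at later on-treatment visits instead of counting as not normalized.

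Some reasons for stopping are linked to ALT. Protocol 7.2 ends treatment on, among other criteria, "Elevation of ALT and/or AST >5x Day 1 or nadir, confirmed by immediate repeat testing". SAP 3.7.2 treats laboratory values as on-treatment only up to two days after the last dose, so a child who stops has no on-treatment ALT value in later visit windows. A reader of the by-visit table would see a percentage on a changing denominator, more favourable than the protocol's rule would give, with no notice that the rule had changed.

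**Working it through.** **1. Figures in the plan.** Neither document states a figure for ALT normalization. The sizing statements concern SVR12, and they reproduce:
- half-width at n = 50 and a rate of 80%: 1.96 × √(0.8 × 0.2/50) = 11.09%, against the stated 11.1%;
- exact power at n = 100, 80% versus 91%, rejecting upward at 89 or more responders: 81.2%, against the stated figure of over 80%.

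Neither depends on the ALT rule.

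**2. Formula.** Take a later on-treatment visit. Let n be the children with baseline ALT above ULN, m those who stopped early and have no value, and r those observed as normal. Assume no other gaps.
- SAP rule: r/(n − m)
- Protocol rule: r/n, because values missing through early stopping are failures
- Ratio (r > 0): [r/(n − m)] / [r/n] = n/(n − m), which is at least 1

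So for early stoppers the SAP rate is never below the protocol-rule rate.

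**3. Size on assumed counts.** The documents give no n, m or r. The values below are assumptions: n = 25 is half of an age group of about 50, and n = 50 is a whole age group.

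| n | m | r | SAP rule | Protocol rule | Difference (points) |
|---|---|---|---|---|---|
| any | 0 | any | r/n | r/n | 0 |
| 25 | 1 | 22 | 22/24 = 91.7% | 22/25 = 88.0% | 3.7 |
| 25 | 2 | 21 | 21/23 = 91.3% | 21/25 = 84.0% | 7.3 |
| 25 | 3 | 20 | 20/22 = 90.9% | 20/25 = 80.0% | 10.9 |
| 50 | 1 | 44 | 44/49 = 89.8% | 44/50 = 88.0% | 1.8 |
| 50 | 5 | 40 | 40/45 = 88.9% | 40/50 = 80.0% | 8.9 |

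The gap grows quickly in small groups. Five stoppers among 25, with 18 normal, would give 18/20 = 90.0% against 18/25 = 72.0%, or 18 points. SAP Table 3-1 splits each age group by genotype, so some cells may hold fewer than 25 eligible children.

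**4. Direction from visit to visit.** Start from 20/25 = 80% and let two children leave, with the others unchanged.

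| Leavers who had normal ALT | SAP rule after | Protocol rule after |
|---|---|---|
| 0 | 20/23 = 87.0% | 20/25 = 80.0% |
| 1 | 19/23 = 82.6% | 19/25 = 76.0% |
| 2 | 18/23 = 78.3% | 18/25 = 72.0% |

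The SAP rate exceeds the protocol-rule rate in every row, but its movement over time depends on who leaves.

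**5. Gaps while still on treatment.** If one of 25 children misses a visit between two normal values and 20 of the other 24 are normal, the SAP gives 20/24 = 83.3% and the protocol 21/25 = 84.0%. For bracketed gaps the SAP rule can therefore be slightly the lower one. The one-sided result in step 2 is for early stoppers.

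**The case against.** **The protocol also contains observed-only rules for laboratory data.** Protocol 9.2.2 drops a subject with a missing safety laboratory result from that time point's summary, and 9.5.4 summarizes observed laboratory data only. ALT is a chemistry analyte, 9.1.3 mentions its normalization only as a possible additional evaluation, and 9.6.3 leaves efficacy details to the SAP. This shows how the SAP rule may have arisen. It does not remove the conflict: those rules concern safety summaries, both documents class ALT normalization as efficacy, and replacing a rule the protocol already states is a change that belongs in SAP 6.4.

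**Missing-as-failure is not the truth either.** This stands. With 21 normal of 23 observed and two missing, the full-group rate lies between 21/25 = 84% and 23/25 = 92%, and the SAP's 91.3% falls inside that range. A reader might infer that the SAP rate is biased upward in absolute terms. The documents support only that, for early stoppers, it is never below the rate under the protocol's rule.

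**Missingness is not wholly tied to ALT.** This also stands. Protocol 3.4 lists reasons for stopping with no stated link to ALT, such as subject request or pregnancy. Children who stop still have chemistry drawn at Early Termination and four weeks post-treatment, and SAP Table 3-4 has a laboratory window for the latter. Their ALT values are absent only from later on-treatment visits.

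**HCV RNA is not handled more strictly for these children.** A reader might infer that ALT was singled out. SAP 3.5.1 also leaves on-treatment HCV RNA missing at visits whose window opens after the last dose. It is stricter only for visits missed while on treatment and for post-treatment visits.

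**Conclusion.** The protocol and SAP conflict on missing ALT normalization values, and SAP 6.4 does not declare the departure. For children who stop early, the SAP rate at later on-treatment visits is n/(n − m) times the protocol-rule rate. The size cannot be derived from the documents. The figures of about 2 to 11 points illustrate the arithmetic under assumed counts and do not show that the effect is material.

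A reader might also infer that the percentage must climb from visit to visit as children drop out. The documents do not support that: it rises only if the leavers were normal less often than those who stay, and it can fall.

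The issue is minor. ALT normalization is reported descriptively without a hypothesis test, and SVR12, its test and the sample size are untouched.

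**What to change.** In SAP 6.2.2, apply the Protocol 9.2.2 rule to ALT normalization. The denominator is all FAS subjects with baseline ALT above ULN. A missing value counts as not normalized unless bracketed by normal values, and values missing after early stopping count as not normalized. Show the observed-only rate beside it, with the numbers observed and missing at each visit.

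If the sponsor prefers to keep the observed-only rate as the main analysis, declare and justify it in SAP 6.4 and add the protocol-rule rate as a sensitivity row.

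The cost is a sentence or two in the SAP and an extra table row with counts. No new data are needed. For early stoppers the protocol-rule figure will be no higher than the current one.
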